6.4 Populations for Analyses

The primary analysis dataset for study outcomes will be the intent-to-treat (ITT) population wherein data from all randomized warts will be analyzed based on the intended randomization assignment. The intent of this protocol is to apply up to 3 sessions of each treatment, but no warts will be

excluded from the ITT population based on the number of treatments actually received. The primary efficacy analysis will be performed using the ITT population. A modified intent-to-treat population will include all warts that received at least one treatment, and the primary efficacy analysis will also be calculated for this population for comparison. The modified ITT population will be the analysis population for the primary safety endpoint.

Study outcomes will also be analyzed using a per-protocol (PP) population. The PP population includes all subjects who had no pre-specified inclusion and exclusion violations, received either CellFX or Cryosurgery, and repeated the treatments per protocol for any warts classified as “not resolved” at the 30-day and/or 60-day visit.

6.5 Sub-Group Analyses

Primary and secondary endpoints will be evaluated for the ITT and PP populations, as well as analyzed in strata based on the following sub-groups:

- Number of treated warts (2 to 4 or 5-8)
- Age
- Prior treatment for treated warts
- Gender
- Clinical Site
- Treatment Energy Level
- Size of CellFX Treatment Tip
- Total Energy Density
- Number of Treatments

These analyses are meant to assess consistency of treatment effects only, and this study is not powered for inference within subgroups.

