3.2 Study Design

This study is designed as a prospective, multicenter, single-blinded, randomized comparison IDE study between CellFX System and Cryosurgery. The Principal Investigator will select a sub-investigator to be the blinded investigator to classify the healing characteristics and wart clearance and/or reduction assessment of each subject's selected warts at baseline, post treatment and at 7-days, 30-days, 60-days, and 90-days following the last CellFX treatment or Cryosurgical procedure. This sub investigator will be blinded to the treatment assignment. The subject may not be blinded to the treatment assignment. The Principal Investigator can choose to be the blinded investigator and select a sub investigator to be the treating investigator.

Eligible subjects with a minimum of 2 and up to 8 warts meeting the inclusion and exclusion criteria will be enrolled. If the subject has more than 8 warts, the subject is excluded from the study. Warts may be present anywhere on the face except the scalp, nose and within the orbital region of the face. Plantar warts are also excluded. Subjects will be randomized to receive either a CellFX treatment or Cryosurgery. Selected warts for each treatment modality must be clearly separated in distance from each other so that wart treatment and side effects can be assessed by the blinded site investigator.

All eligible warts will receive at least one CellFX or Cryosurgical treatment. Each subject will be evaluated by the blinded site investigator at 7-days, 30-days, 60-days, and 90-days post-initial CellFX and Cryosurgical treatments. At the 30-day or 60-day follow-up visit, if any wart is classified as “not resolved”, the wart must receive an additional treatment. In case of a second or third retreatment, the subject will be evaluated by the blinded site investigator at 30-days, 60-days, and 90-days post-retreatment. Photography of the warts will be captured along with the blinded site investigator assessments at all visits.

Numbness (diminished/ altered sensation) Assessment: The treating investigator will conduct a “light touch” exam to all treated areas at baseline, 7 days and 30 days post initial treatment and 30 days post retreatment(s). Light touch is tested with a cotton wisp, feather, and/or even light finger touch. The subject will be asked how one area feels compared to another.

Note 1:

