Eligible warts that should be treated and do not receive a retreatment will be considered a protocol deviation. The reason(s) for not receiving an additional treatment will be collected on the electronic case report form (eCRF). These subjects will remain in the study and will be included in the ITT population.

Additionally, subjects can only receive two additional treatments or up to a maximum of three CellFX or Cryosurgical procedures.

Non-Treated Wart Criteria: Data will be collected on ineligible or non-treated warts for all enrolled subjects. Non-treated warts are defined as flat, periungual, subungual, mosaic, plantar, filiform and/or common warts that are excluded due to anatomic location. Photography of the non-treated warts will be captured at baseline and the last study visit.

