3.8 Clinical Study Duration

It is anticipated that the enrollment of subjects in this study will take approximately 3-4 months in duration. All subjects who only receive one treatment will return for follow-up visits at 7-days, 30 days, 60-days, and 90-days or up to a total of 5 study visits. For subjects who receive additional CellFX or Cryosurgery retreatments, at the 30-day or 60-day follow up visit, will return for additional follow-up for 90-days post last treatment or up to a total of 6 or 7 study visits. The total study duration will be approximately 9 months.

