- Photographic images of all treated warts will be taken with pre- and post-wart markings
- All warts will be clinically assessed by the blinded site investigator (wart healing characteristics, wart clearance and wart reduction assessments)
- Assessment of numbness in the treated area will be performed by the treating investigator

- If any wart is classified as “not resolved”, a second treatment with CellFX or Cryosurgery will be performed to the previously treated wart(s)

In case of a second CellFX or Cryosurgical treatment is required:

- Local anesthesia/numbing will be applied to each wart designated for a CellFX retreatment
- Each wart designated for a CellFX retreatment will be treated using pre-determined energy settings
- Each wart designated for Cryosurgical retreatment will be performed as outlined in protocol **Section 3.5**
- The subject will be asked to rate his/her pain immediately after each wart treated with CellFX and/or Cryosurgery by using a numerical rating score
- The subjects will be asked whether they felt muscle twitching immediately after each lesion treated with CellFX
- Immediately post-procedure, a wart healing characteristics assessment will be performed by the blinded site investigator
- Photographic images of all retreated warts will be taken post-treatment
- A light bandage and/or any physician recommended dressing may be applied before the subject leaves the clinic
- Any adverse events will be identified and documented with a live assessment by the blinded site investigator

4.8 60-Day Follow-up Visit (CellFX/Cryosurgical Treatment #3, if required)

- Photographic images all treated warts will be taken with pre- and post-wart markings
- All warts will be clinically assessed by the blinded site investigator (wart healing characteristics, wart clearances and wart reduction assessments)
- Assessment of numbness in the treated area will be performed by the treating investigator (only for those subjects who received a retreatment at the 30-day follow-up visit)

- If any wart is classified as “not resolved”, a third treatment with CellFX or Cryosurgery will be performed to the previously treated wart(s)

In case of a third CellFX or Cryosurgical treatment is required:

- Local anesthesia/numbing will be applied to each wart designated for a CellFX retreatment
- Each wart designated for a CellFX retreatment will be treated using pre-determined energy settings

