6.1 Co-primary Endpoints

Clinical acceptance of treatment with the CellFX System for common warts requires non-inferior clearance response (effectiveness), non-inferior healing processes and non-inferior rates of adverse skin changes (safety) versus cryosurgery. Because these features are critically important for treatment acceptability, this study is designed with 3 co-primary endpoints. The endpoints must demonstrate non-inferiority for the study to be considered successful.¹¹

All 3 co-primary endpoints are assessed with wart as the unit of analysis, but the analyses will be adjusted for within-subject correlation. The co-primary safety endpoints are the proportion of warts with adverse events related to wound healing (scabbing, swelling, crusting, blister, scar or ulcer) at 30 days after the last treatment and adverse skin changes (the presence of hyperpigmentation, hypopigmentation or scarring) at 90 days post last treatment. The co-primary effectiveness endpoint is the proportion of warts classified as “resolved” at 30 days post last treatment.

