6.1.2 Primary Effectiveness Endpoint

The primary effectiveness endpoint is wart clearance, defined as “resolved” versus “not resolved” at 30 days following the last CellFX or Cryosurgical treatment (30 days post-last treatment) based on the classification of the blinded site investigator. The timing of the evaluation of this endpoint is wart specific as some warts may not require more than 1 treatment with the CellFX System or Cryosurgery. The investigator, blinded to treatment assignment, will classify each wart as “resolved” or “not resolved”.

The primary effectiveness analysis will be a comparison between CellFX and Cryosurgical treatment groups based on 30-day post treatment clearance rate, defined as the proportion of warts classified as “resolved”. This binary outcome classifies warts as completely clear versus not completely clear. The 30-day time-point was selected to reduce the impact of spontaneous wart resolution unrelated to treatment.

The statistical hypotheses to be evaluated for the primary efficacy endpoint are:

$H_0: p_{CellFX} - p_{Cryo} \leq -15\%$ at 30 days post last treatment, versus

$H_A: p_{CellFX} - p_{Cryo} > -15\%$ at 30 days post last treatment

Where p_{CellFX} and p_{Cryo} are the proportion of warts classified as “resolved” in each treatment group. The null hypothesis will be rejected if the lower bound of the 2-sided 95% confidence interval for the difference in proportions ($p_{CellFX} - p_{Cryo}$) is greater than -15%, which is equivalent to a 1-sided test with a 2.5% type I error rate.

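### Section 6.5 uses the number of treatments as a subgroup factor to judge consistency of effect, but response to treatment sets that factor after randomisation

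*Combined protocol and SAP*

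**What the plan says.** Section 6.5 lists nine factors by which the primary and secondary endpoints will be analysed in strata, alongside the ITT and PP analyses. One is "Number of Treatments". The stated purpose is: "These analyses are meant to assess consistency of treatment effects only". The section adds that the study lacks power for inference within subgroups.

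Three other parts of the protocol determine what this factor means:

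- **Retreatment.** Under Section 3.2, if a wart is rated not resolved at the Day 30 or Day 60 visit, "the wart must receive an additional treatment". Sections 4.7 and 4.8 repeat this for the second and third sessions. Three sessions is the maximum.
- **Endpoint.** Section 6.1.2 defines primary effectiveness as the blinded site investigator's rating "at 30 days following the last CellFX or Cryosurgical treatment", timed separately for each wart.
- **Counting unit.** Section 6.5 gives none. Section 6.1 says "All 3 co-primary endpoints are assessed with wart as the unit of analysis". Note 1 of Section 3.2, however, says "subjects can only receive two additional treatments", and Section 3.8 writes "All subjects who only receive one treatment will return for follow-up visits"; both count by subject.

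**The concern.** A consistency check asks whether the randomised treatment effect is similar across groups defined before treatment. The number of treatments is not such a group. It records how the wart responded to the assigned device, so it is itself an outcome of randomisation.

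For primary effectiveness the link is closer still, because the rating that ends treatment is the endpoint rating. The early strata are therefore fixed in advance, and the last stratum holds the warts (or subjects) that the assigned device had failed to clear by Day 60. A zero difference in the early strata could be read as agreement between the arms when it carries no information. The contrast in the last stratum could be read as a treatment effect when the two groups compared are no longer those formed by randomisation. The caveat about power does not help, because it concerns precision and a larger trial would have the same problem.

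**Working it through.** **1. Tracing the rule, with no assumed rates.** Take a wart handled as Sections 3.2, 4.7 and 4.8 require.

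| Course of the wart | Endpoint visit | Primary result |
|---|---|---|
| Treated at Day 0 only | Day 30 | Resolved; otherwise it would have been retreated |
| Treated at Days 0 and 30 only | Day 60 | Resolved; otherwise it would have been retreated |
| Treated at Days 0 and 60 (resolved at Day 30, recurred by Day 60) | Day 90 | Either |
| Treated at Days 0, 30 and 60 | Day 90 | Either |

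The one-treatment stratum is thus 100% against 100%, whether treatments are counted per wart or per subject. The two-treatment stratum is the same apart from recurrences first retreated at Day 60. The PP definition in Section 6.4 requires that the rule was followed. In ITT, a one-treatment failure needs either a retreatment that was not given or a result produced by missing-data handling. Note 1 of Section 3.2 makes the missed retreatment a deviation, and Section 10.3.2.1 foresees scab or crust that would prevent it.

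Secondary endpoint 2 (resolution 30 days after the first treatment) is also 100% against 100% in the one-treatment stratum. In the three-treatment stratum it is 0% against 0% if treatments are counted per wart. Counting per subject mixes in sibling warts that cleared early.

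The photographic-panel, 60-day and over-time resolution endpoints and the safety endpoints are not fixed by the stratum. Their strata are still formed after randomisation, so the arms are not comparable within them.

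**2. Size at the planned rates.** From Section 6.3: clearance 75.5% (CellFX) and 70% (cryosurgery), 3 warts per subject, within-subject correlation 0.3. Assumptions added here: constant clearance per session and no recurrence.

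*Per wart.* Per-session clearance is c = 1 − (1 − P)^(1/3).
- CellFX: 1 − 0.245^(1/3) = 37.4%. Cryosurgery: 1 − 0.30^(1/3) = 33.1%.
- Share of warts with 1, 2 and 3 treatments: 37/23/39% (CellFX) and 33/22/45% (cryosurgery).
- Stratum differences: 0, 0 and +4.4 points (unrounded rates), against +5.5 overall.
- With CellFX exactly at the non-inferiority margin (55% against 70%), the first two strata still show 0. The third shows 23.4% − 33.1% = −9.7, against −15 overall.

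*Per subject.* A Gaussian threshold model (a further assumption) gives the warts of a subject a latent correlation of 0.490 (CellFX) and 0.475 (cryosurgery), set so that final clearance has correlation 0.3.
- P(third session) = 1 − P(all 3 warts clear by Day 60) = 64.3% and 70.7%.
- Every failure lies in this stratum, so primary clearance is 1 − 0.245/0.643 = 61.9% and 1 − 0.30/0.707 = 57.6%, a difference of +4.3.
- Secondary endpoint 2 in this stratum is 18.9% against 17.8%.
- If warts are independent: P(third session) 77.5% and 83.2%, primary clearance 68.4% and 63.9% (+4.4), secondary endpoint 2 30.4% against 27.6%.

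**3. How far the last stratum can move while the overall effect stays at +5.5.** Let eC and eK be clearance by Day 60, in percent. The protocol gives neither, so both are assumed. Per wart, the last stratum clears (75.5 − eC)/(100 − eC) against (70 − eK)/(100 − eK). With eC = 65, CellFX clears 10.5/35 = 30.0% per wart, and 58.9% per subject under the threshold model.

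| eK | Cryosurgery, per wart | Difference | Cryosurgery, per subject | Difference |
|---|---|---|---|---|
| 65 | 14.3% | +15.7 | 50.0% | +8.9 |
| 60 | 25.0% | +5.0 | 54.3% | +4.5 |
| 55 | 33.3% | −3.3 | 57.7% | +1.2 |
| 50 | 40.0% | −10.0 | 60.4% | −1.5 |
| 40 | 50.0% | −20.0 | 64.2% | −5.4 |

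Per-subject differences use unrounded values. The sign changes at eK = 100 − (30/24.5) × 35 = 57.1 per wart and at 53.0 per subject. With independent warts the per-subject range is +7.6 to −1.7, with the change at 48.2.

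**4. CellFX-only factors.** Energy level, tip size and energy density, also listed in Section 6.5, belong to the CellFX procedure (Section 3.4). They have no counterpart under cryosurgery and cannot form strata for a between-arm comparison.

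**The case against.** The strongest reply is that nothing turns on these tables. The primary ITT analysis drops no wart for the number of treatments it received (Section 6.4), success rests on the co-primary endpoints alone (Section 6.1.4), and Section 6.5 disclaims inference. A 100% against 100% table is plainly structural. Secondary endpoints 2 and 6 already give unstratified early-response comparisons without this problem. All of this stands, and it is why the point is minor. It does not make the factor fit for the stated purpose.

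The wart is also the natural counting unit: Section 6.4 speaks of treatments received by warts, and endpoint timing is wart-specific. That is fair, but Section 6.5 should still say so. The one-treatment result is the same under either count.

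The assumed rates are open to challenge. The −20 extreme needs cryosurgery to clear about 22.5% per session in the first two sessions (1 − √0.60) and then 50% of the warts that remain, and nothing in the protocol supports rising response among repeat failures. The milder reversal at eK = 55 does not need this (32.9% per session, then 33.3%).

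The constant-rate model also sits poorly with the earlier CellFX data in Section 1.5. If the 63 single-treatment common warts are among the 93, one session cleared at least 51/93 = 54.8%, and retreated warts cleared 21/30 = 70%. Those data used a different response (more than 90% size reduction at 60 days) and optional retreatment. The models here are illustrations, and the structural result does not depend on them.

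Finally, Section 6.0 refers to a separate SAP that was not supplied. It may already treat this factor as descriptive.

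**Conclusion.** The concern holds and is minor. As Section 6.5 is written, strata of number of treatments cannot show whether the treatment effect is consistent. For primary effectiveness and secondary endpoint 2, the one-treatment difference is zero by construction, given only that the retreatment rule is followed. The last stratum compares groups selected by earlier failure.

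Under constant per-session clearance its contrast is about one point from the overall effect under either count. Under other assumed Day 60 clearances it ranges from +15.7 to −20.0 per wart and from +8.9 to −5.4 per subject. A change of sign is possible but not shown to be likely. For the remaining endpoints the fault is loss of comparability between arms, not a fixed result. Confidence is high on the structure; the sizes rest on the stated assumptions.

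**What to change.** In Section 6.5:

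- Remove number of treatments from the factors used to assess consistency between arms, and report its distribution by arm as an outcome. That comparison keeps the randomised groups intact.
- Keep any table by number of treatments, including safety by number of sessions, as descriptive only, and state whether the count is per wart or per subject.
- Label energy level, tip size and energy density as descriptive summaries within the CellFX arm.
- If the separate SAP already does this, align Section 6.5 with it.

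The cost is protocol and SAP wording. All the variables are already collected, and the co-primary tests, power and sample size do not change.

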6.6 Missing Data

All possible efforts will be made to minimize missing data in this study. Based on previous studies, any missing data that does occur is likely due to missed follow-up visits, so all study warts for subjects with a missed visit will have missing endpoints. The timing of the co-primary effectiveness and wound healing events at 30 days should minimize missed visits related to study fatigue. The generalized estimating equation model can yield valid results when data are missing completely at random, and the sensitivity analysis using a mixed model can yield valid results when data are missing at random. Additionally, the sensitivity of the final results to missing data for the skin change safety outcome will be examined by comparing the primary outcomes to the results using a longitudinal model with both the 30-day, 60-day and 90-day post treatment results, and a tipping-point analysis will be performed for the endpoints at 90 days to determine whether the missing data could change the inference compared to the primary models.

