6.1.1 Co-primary Safety Endpoints

The wound healing safety endpoint is the presence or absence of a wound healing safety event at 30 days from the last CellFX or Cryosurgical treatment as assessed by the blinded site investigator. The wound healing safety event is defined as the presence of scabbing, swelling, crusting, blister, scar or ulcer. The timing of the evaluation of this endpoint is wart specific as some warts may not require multiple treatments with CellFX or Cryosurgery. Warts will be categorized as having a primary safety event if any component (scabbing, swelling, crusting, blister, scar or ulcer) is present at the follow-up visit 30 days after the last treatment.

The statistical hypotheses to be evaluated for the wound healing primary safety endpoint are:

$$H_0: p_{CellFX} - p_{Cryo} \geq 15\% \text{ at 30 days post last treatment, versus}$$

$$H_A: p_{CellFX} - p_{Cryo} < 15\% \text{ at 30 days post last treatment}$$

Where p_{CellFX} and p_{Cryo} are the proportion of warts with a composite wound healing safety event (scabbing, swelling, crusting, blister, scar or ulcer) in each treatment group. The null hypothesis will be rejected if the upper bound of the 2-sided 95% confidence interval for the difference in proportions ($p_{CellFX} - p_{Cryo}$) is less than 15%. This approach is equivalent to a 1-sided test with a 2.5% type I error rate.

The skin change safety endpoint is the presence or absence of a skin change safety event at 90 days from the last CellFX or Cryosurgical treatment as assessed by the blinded site investigator. The skin change safety event is defined as the presence of hyperpigmentation, hypopigmentation, or scarring. The timing of the evaluation of this endpoint is wart specific as some warts may not require multiple treatments with CellFX or Cryosurgery. Warts will be

categorized as having a skin change safety event if any component (hyperpigmentation, hypopigmentation, or scarring) is present at the follow-up visit 90 days after the last treatment.

The statistical hypotheses to be evaluated for the skin change primary safety endpoint are:

$H_0: p_{CellFX} - p_{Cryo} \geq 15\%$ at 90 days post last treatment, versus

$H_A: p_{CellFX} - p_{Cryo} < 15\%$ at 90 days post last treatment

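### Section 6.6 treats a missed visit as losing all of a subject's warts, but the 30-day co-primaries are read wart by wart, so loss after Day 30 removes only retreated warts and is not missing completely at random

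*Combined protocol and SAP*

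**What the plan says.** Section 6.6 expects any missing data to come from missed visits, "so all study warts for subjects with a missed visit will have missing endpoints". On the primary model it says: "The generalized estimating equation model can yield valid results when data are missing completely at random". It also names a mixed model as a sensitivity analysis valid under missing at random (MAR), without giving its terms.

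Two further analyses are limited in scope. The longitudinal model appears where "the sensitivity of the final results to missing data for the skin change safety outcome will be examined", and "a tipping-point analysis will be performed for the endpoints at 90 days".

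The endpoint rules stand elsewhere:
- **Clearance (6.1.2)** is scored 30 days after the last treatment: "The timing of the evaluation of this endpoint is wart specific as some warts may not require more than 1 treatment". Section 6.1.1 gives wound healing the same wart-specific 30-day timing.
- **Skin change (6.1.1)** counts as an event if "any component (hyperpigmentation, hypopigmentation, or scarring) is present at the follow-up visit 90 days after the last treatment", again timed per wart.
- **Retreatment (3.2)** follows the interim reading: for a wart not resolved at Day 30 or Day 60, "the wart must receive an additional treatment". Sections 4.7 and 4.8 apply this at the two visits.

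Section 6.3 allows for about 15% loss to follow-up. Section 6.0 defers analysis details to a separate SAP, whose text is not in the supplied document.

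**The concern.** If all warts of a lost subject were missing together, whatever their status, dropping them would do little harm when loss is unrelated to outcome. The endpoint rules do not work that way. After Day 30, the 30-day results still outstanding belong only to warts recorded as unresolved and then retreated. Even if the decision to leave is pure chance, which warts go missing depends on their recorded Day-30 or Day-60 status. The MCAR condition in 6.6 then fails at wart level.

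Section 6.6 also argues that the 30-day timing should limit missed visits. For a retreated wart, 30 days after last treatment is about study Day 60 or Day 90.

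At stake is the clearance non-inferiority test (margin 15 points, one-sided 2.5%). Section 3.2 says subjects may know their assignment, so unequal loss cannot be excluded, although nothing in the documents predicts it.

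**Working it through.** **1. Plan's loss allowance.** Section 6.3 needs 63 subjects per arm. 2 x 63 / 0.85 = 148.2, so 149, against 150 stated. That gives 75 per arm. No plan figure is disputed here.

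**2. Which 30-day results are lost**

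| Visit pattern | Wart resolved at Day 30 | Wart retreated at Day 30 or 60 |
|---|---|---|
| Permanent loss before Day 30 | missing | missing |
| Permanent loss between Day 30 and the endpoint visit | kept | missing |
| Misses Day 30 only, returns at Day 60 | no 30-day reading | can be treated at Day 60 and read at Day 90 |

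Only the first row matches 6.6. For skin change the same split arises after Day 90: once-treated warts have been read, while retreated warts are due at Day 120 or 150.

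**3. Bias by hand, permanent loss just after Day 30.** Let P be true clearance, s the proportion of warts cleared by the first treatment, and d the loss. Then

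observed = [s + (P - s)(1 - d)] / [s + (1 - s)(1 - d)].

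Assume s = 0.71P. The 71% is 51/72, from the previous CellFX study in Section 1.5: 51 of 63 once-treated and 72 of 93 of all common warts. That study used more than 90% size reduction at 60 days and optional retreatment. No source exists for cryosurgery, so 50-85% is also run.

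At the margin (55% v 70%), with loss 20% CellFX / 10% cryosurgery:
- CellFX: s = 0.3905; 0.5181 / 0.8781 = 59.0%.
- Cryosurgery: s = 0.497; 0.6797 / 0.9497 = 71.6%.
- Difference -12.6 points against a true -15.0 (shares 50-85%: -13.2 to -12.2).
- With 15/15 the difference is -14.5.

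An exchangeable GEE moves somewhat further, because it gives more weight per wart to subjects with few observed warts.

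**4. Simulation with the GEE.** 75 subjects x 3 warts per arm, within-subject correlation about 0.3 (Section 6.3), exchangeable identity-link GEE with sandwich SE, true difference -15 points. Spread loss is uniform over each subject's own course to Day 90, 120 or 150. There were 20,000 trials for the base case and 12,000 for other shares. Difference ranges cover shares of 50-85%.

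| Loss, CellFX/cryo | Spread: difference | Spread: type I | All in Day 30-90: difference | All in Day 30-90: type I |
|---|---|---|---|---|
| none | -15.0 | 2.6% | | |
| 15/15 | -14.8 (-14.6 to -15.0) | 2.6-3.0% | -14.2 (-13.8 to -14.9) | 2.8-3.8% |
| 17/13 | -14.3 to -14.5 | 3.1-3.3% | | |
| 20/10 | -13.9 (-13.8 to -14.2) | 3.6-4.2% | -11.7 (-11.4 to -12.5) | 6.3-8.8% |
| 10/20 | -15.5 (-15.3 to -15.7) | 1.8-2.1% | -16.8 (-16.1 to -17.1) | 0.9-1.8% |

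Repeat simulations at 20/10 gave 3.6% and 4.5% (spread), and 8.0% and 7.7% (early loss). At the planned 75.5% v 70% with 15/15 loss, each arm rises by about 1 point (spread) or 3 points (window). The difference stays at 5.3-5.5 or 4.9-5.6, against a true 5.5.

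**5. Opposite direction.** Suppose 5% of subjects miss only Day 30, no Day-60 reading is substituted, and 60% of later clearances come at the next treatment. At P = 0.70 and s = 0.497:

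observed = (0.95 x 0.70 + 0.05 x 0.1218) / (1 - 0.05 x 0.497) = 0.6711 / 0.9752 = 68.8%, a fall of 1.2 points.

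If all later clearances are still achieved, the fall is 0.8.

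**6. Does imputation repair it?** Retreated warts were imputed within arm from Day-30/Day-60 status (10 imputations, 8,000 trials, 71% share). The difference returned to -15.0 to -15.2 and type I error to 2.4-2.8% under both loss timings. The SE was 5.80 points, against 5.86 observed-case (20/10, spread). These runs had permanent loss only.

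**The case against.** **Materiality.** With equal, spread loss the effect is close to nil. The 4% needs two-to-one loss against CellFX, and the 6-9% also needs every loss to fall between Day 30 and Day 90. Under the spread model, 45-47% of leavers go after all clearance results are in. This stands, and it limits the point to a recommended change.

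**Direction.** A reader might infer that observed clearance is always too high. The documents do not support that: 6.6 speaks of missed visits, and a subject who misses only Day 30 pulls clearance down by a similar amount (step 5). The upward bias belongs to permanent loss.

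**Safeguards.** A reader might also infer that no planned analysis covers clearance. That can be said only of the supplied text, because the SAP could not be checked. The MAR mixed model is not restricted to skin change and would help if it conditions on interim status; 6.6 does not say whether it does, and it was not simulated here. The secondary analysis of resolution after one treatment is read at Day 30, so later loss does not affect it.

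**Status of the sentence.** It states an expectation, not an analysis rule, so rewording it alone changes no estimate. That is true, but the expectation supports the choice of missing-data methods.

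**Conclusion.** The point holds. For clearance and wound healing, the statement in 6.6 that all of a subject's warts go missing is right for permanent loss before Day 30 and wrong for later loss. It is wrong for 90-day skin change when loss falls after Day 90. Wart-level missingness then depends on recorded interim status and is not MCAR.

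For the clearance test the size is minor to moderate: type I error about 3% with equal spread loss, about 4% at 20/10 spread, 6-9% at 20/10 with all loss between Day 30 and Day 90, and below 2.5% if the imbalance is reversed. Loss timing, arm split and the first-treatment share are assumptions. No size was computed for wound healing or skin change.

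A reader might take these rates as the chance of a false study success. They are not: all three co-primaries must pass, so the study-wide rate is lower.

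**What to change.** In Section 6.6:

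1. Replace the sentence on all study warts with a wart-specific one, for example: *Missing endpoints are wart-specific. After permanent loss later than Day 30, the 30-day endpoints are missing only for retreated warts not yet assessed 30 days after their last treatment. Warts resolved earlier keep their 30-day results but may lack the 90-day skin-change result. If only the Day-30 visit is missed, the 30-day results of warts that need no further treatment are missing.*
2. Pre-specify a sensitivity analysis for clearance, and in the same way for wound healing. Multiply impute within arm any wart with a missed endpoint visit, using recorded Day-30/Day-60 status and number of treatments, then fit the same GEE. Alternatively, state that the planned mixed model already conditions on that status, if it does.
3. Extend the planned tipping-point analysis to clearance, varied separately by arm.

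Cost: plan wording, an imputation model to specify, some programming, and possibly a slightly wider confidence interval. No new data are needed, since Table 2 already collects resolution status at Visits 3 and 4.
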